4.7.2 Treatment with RePneu Coils

Subjects will undergo bronchoscopy under general anesthesia or moderate sedation, at the discretion of the bronchoscopist. During the procedure, subjects will be treated with Coils according to the Instructions for Use, according to CE Mark intended use. Subjects will receive prophylactic drugs as prescribed by the protocol.

Following RePneu Coil placement at Treatment 1 (Tx1) and Treatment 2 (Tx2), the subject will remain in the hospital under observation per standard hospital practice. Following hospital discharge, the subject will be seen at the study site at one month after Tx1. After the one month visit following Tx1, the subject will complete the Tx2. Only a single lung will be treated during either of the first 2 bronchoscopies.

After Tx2, the subject will remain in the hospital under observation per standard hospital practice. Following hospital discharge, the subject will be seen at the study site at one month post Tx2.

If, at the discretion of the treating investigator and in consultation with the patient, the patient did not respond to the bilateral treatment possibly due to low coil dose determined at Visit 3 (1 month post Tx2), an optional Tx3 may be scheduled to place an additional 1-3 coils bilaterally. The investigator will determine whether the patient anatomy (large lung, large lobe, diffuse large volume damage) warrants an additional 1-2 coils in each upper lobe or 1-3 additional coils in each lower lobe. The exact number of addition coils is at the discretion of the investigator.

The procedures shall be performed no closer together than 4 weeks and if possible no longer than 8 weeks apart.

The follow up visits should be performed at 4 months post final treatment and 1 year post treatment 1.

Follow-up visits will occur at the hospital which performed the coil implantation procedure.

Treatment Planning Chart

		Upper Lobe Character Score						
		0	1	2	3	4	5	
Lower Lobe Character Score	0	U	U	U	U	U	NT	
	1	L	U	U	U	U	NT	
	2	L	L	U	U	U	NT	
	3	L	L	L	U	NT	NT	
	4	L	L	L	NT	NT	NT	
	5	NT	NT	NT	NT	NT	NT	

U – Upper lobe treatment with approximately 10 coils per lobe

L – Lower lobe treatment generally between 11 and 14 coil per lobe

NT – Patient not eligible, do not treat

- A) Evaluate the CT independent data to diagnose COPD and possibly exclude the patient from safe use of the coiltechnology.
- B) Review the patient's CT for indicators of disease that may exclude the patient from treatment (**study site responsibility**) such as:
 - a. Clear visible bronchiectasis in the treatment lobe
 - b. Scarring/ fibrosis in the treatment lobe
 - c. Unstable or suspicious nodule in any lobe
 - d. Severe bullous disease

Steps C-E will be performed by PneumRx and by the treating site. Decisions related to treatment planning will be by agreement between the site investigator and PneumRx.

- C) Review the patient's CT and assign a character score for each lobe. The right upper, left upper, right lower and left lower lobe should be evaluated and a character score should be recorded for each lobe. The score should be based on a review of all the slices that comprise the lobe. The score should characterize the average damage of the most severe slice within each lobe as detailed above (not an average of the entire lobe).
- D) Interpret the character score to recommend a treatment plan or to exclude the patient using the following guideline:
 - a. If the any of the 4 major lobes receive a score of 5, the patient should be excluded from the study.
 - b. If either lung presents with a score of 4 and 4 or a combination of 3 and 4, the lung is in a severely damaged homogeneous condition and the patient should be excluded.
 - c. The treatment planning chart should be reviewed to determine a treatment plan for each lung. Treatments should be upper or lower lobes, or opposite upper/lower lobe pairs (i.e. left-upper and right-lower lobes) but not both lobes in a single lung, except for the optional Tx3. The treatment plan should recommend treatment in the lobe with the highest character score in each lung as indicated by the treatment planning chart.
- E) Heterogeneous or Homogeneous?

Patients will be classified as heterogeneous or homogeneous by comparing the character score of the evaluable lobes in each lung. A character score difference between the upper versus lower lobe greater than 1 (2 and above) indicates heterogeneous damage in that lung. A lung with character scores that match or are different by 1 point is considered homogeneous. A patient that presents both lungs as homogenous is considered homogeneous. All other patients are considered heterogeneous (a patient with both types is considered heterogeneous).

4.7.3 Pharmacological Treatment

As recommended by the GOLD guidelines, each subject will continue maintenance bronchodilator therapy, which will include an inhaled long-acting beta agonist, inhaled anticholinergic, or both. These drugs may also be combined with theophylline and/or inhaled corticosteroids at the discretion of the treating physician. The physician will be allowed to adjust the subject's pharmacological regimen as needed during the course of the study to deal with variations in the subject's condition (e.g., COPD exacerbations). However, the subject's medical regimen should be optimized at the pre-Treatment Visit, prior to completing the baseline Six Minute Walk Test and pulmonary function tests. Medically necessary changes in medications or dosages will be recorded in the CRF. Supplemental oxygen utilization should be recorded and monitored throughout the Study.

All subjects enrolled in the study must have current influenza and pneumococcus vaccinations consistent with local recommendations and/or policy.

Prophylactic anti-inflammatory treatment with steroids 50mg/day shall be given 1 day prior, during and after each treatment for up to 15 days. Prophylactic treatment with antibiotics can be considered for at least 5 days if some bleeding occurs during the implantation and there are infiltrations on chest x-ray post Tx or patient has an excess secretion or sputum culture shows pathologic concentration. Pseudomonades effective antibiotics are needed only in case of positive culture in sputum.

Table 3. Visit Schedule

Procedure / Assessment	Visit 1 Baseline Screening (at least 7 days prior to Tx1)	Tx1 RePneu Placement	Visit 2 1 month post Tx1	Tx2 RePneu Placement (4-8 weeks post Tx1)	Visit 3 1 month post Tx2	Optional Tx3 RePneu Placement (4-8 weeks post Tx2)	Visit 3 4 months post final Tx	Visit 4 12 months post Tx1
Informed Consent	X							
Inclusion/ Exclusion	X							
Focused physical exam including vital Signs and SpO ₂	X	X	X	X	X	X	X	X
Spirometry	X						X	X
Lung volumes	X						X	X
6MWT	X						X	X
SGRQ	X						X	X
mMRC	X						X	X
Concomitant medication / O ₂ Use	X	X	X	X	X	X	X	X
Pregnancy testing	X	X		X		X		
Physical activity and energy expenditure for 6-8 days	X						X	X
Bronchoscopic still images			X		X		X	
Static and dynamic pulmonary compliance prior and post Tx			X		X		X	
Echocardiogram	X						X	X
Body composition	X						X	X
V/P SPECT or Lung perfusion scintigraphy	X							X
High Resolution CT	X							X
Chest X-Ray	X	X		X		X		
Bronchoscopy / Coil Placement			X		X		X	
Adverse Events	X	X	X	X	X	X	X	X

5 Study Subject Recruitment

All study subjects will be patient volunteers who are diagnosed with emphysema and who meet the inclusion / exclusion criteria including a willingness to read, understand, and sign the Informed Consent.

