There are several treatments available for emphysema including smoking cessation, medications, physical therapy, supplemental oxygen, and surgery. Emphysema can be treated with inhaled bronchodilators, inhaled corticosteroids, anticholinergics, theophylline, phosphodiesterase-4 inhibitors and supplemental oxygen. Emphysema patients are prone to exacerbations, usually due to respiratory infections, which are usually treated with antibiotics and/or systemic corticosteroids and frequently require emergency room visits and/or hospitalizations. Emphysema patients may undergo pulmonary rehabilitation exercises and training. There are also two surgical procedures available for treatment of severe emphysema: lung transplantation and lung volume reduction surgery (LVRS). Lung transplantation is a seldomly used option because of the limited availability of donor lungs, low transplantation priority for emphysema patients relative to other rapidly fatal pulmonary diseases, and because of the advanced age of most emphysema patients. Lung Volume Reduction Surgery is major surgery that carries the risk of morbidity and mortality. Recently, less invasive bronchoscopic approaches have been developed and several approaches are being actively investigated in human clinical trials in Europe and the US but none of them are indicated for use in homogeneous type of emphysema.

The PneumRx RePneu Coil is designed to compress the areas of lung parenchyma most damaged by emphysema. This compression reduces air flow to treated portions of the lung allowing enhanced airflow to healthier untreated portions of the lung (Figure 1). The compression also reduces the volume of the hyperinflated emphysematous lung, resulting in lung volume reduction with improved diaphragmatic efficiency. Additionally, by gathering up the loose parenchyma of the most severely damaged segments, the Coil restores elasticity and recoil to the whole lung, improving expiratory flow rates, lessening small airway collapse with air trapping, and reducing dynamic hyperinflation. Because

the Coil acts by a simple mechanical action these effects are achieved immediately in the presence or absence of collateral ventilation. This device is deployed using a minimally invasive approach using a simple catheter-based delivery system through a fiber-optic bronchoscope and requires no incision.

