6.1 Investigator Training

Investigators will have been trained and/or re-trained in the proper use and operation of the RePneu System, and will have performed several commercial procedures prior to initiation of any treatment.

PneumRx personnel will be present at the first five treatments for each implanter to provide any additional technical support during treatment sessions, and/or until the investigator and his/her team feel comfortable with the use of the device.

NOTE: All assessments by investigators or other healthcare professionals will be performed to the same standards (ATS/ERS Guidelines) as those in the pivotal protocol as detailed in the Study Operational Instructions.

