6.5 Treatment Tx1, Tx2 and optional Tx3

- Perform pregnancy test for females of child bearing potential prior to radiographic procedures.
- Prepare subject for bronchoscopy per standard hospital practice.
- Prescribe a prophylactic regimen of antibiotics and steroids before and after treatment.
- Administer general anesthesia or sedation to perform Coil placement. All local institutional policies relevant to general anesthesia and/or sedation should be observed.
- Insert the bronchoscope into the subject per the bronchoscope manufacturer's instructions.
- Navigate the bronchoscope and identify the airways leading to the diseased parenchyma via fluoroscopy.
- Insert the Catheter into the working channel of the bronchoscope and deliver the device per the RePneu Coil Instructions for Use.
- Navigate the Catheter to the distal airways and verify the position via fluoroscopy.
- Deliver the Coil into the Catheter and deploy the Coil while monitoring the position via fluoroscopy in accordance with RePneu Coils Instructions for Use.
- Only place the devices unilaterally. DO NOT place the devices in both the right and left lungs during one bronchoscopy session (except for Tx3).
- Allow the subject to recover from anesthesia and monitor as per standard hospital practice.

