**Table 1: Visit Schedule**

## 2 TYPES OF PLANNED ANALYSES

### 2.1 Final analysis

The final analysis shall consist of all analyses described in this document. The details of the analyses are described in section 4. Additionally, Appendix I: Overview of tables, figures and listings to be produced provides an overview of all tables, plots and listings to be produced as well as the appropriate analysis set.

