## 4 CHANGES COMPARED TO THE PROTOCOL

This SAP contains the following changes compared to the protocol:

1. The follow up visits shall be performed 3 months post final treatment and not 4 months post final treatment as stated in the protocol
2. No Subgroup Analyses will be done.
3. The ITT Analysis will consider subjects with unilateral treatment. There will not be a per-Protocol analysis.
4. Due to very slow recruitment the study was prematurely terminated. Given the limited number of patients included in the database, compared to the plan the following data was not entered into the database and subsequently not analysed for the following endpoints:
  1. Geometry (roundness) of major lung airways as defined by the ratio of major versus minor diameter measured from 3 bronchoscopic still images prior and post procedure taken in the lobar airway of the carina leading to segmental airways or while in any segmental airways of the same lobe of the carina leading to sub-segmental airways)
  2. Static and dynamic pulmonary compliance measurement prior to and post treatment including closing volumes, closing capacity and small airways function
  3. Physical activity and energy expenditure measured over a period of a week using multi-axial accelerometer.
  4. heart ejection fraction, systemic blood pressure
  5. fat per mass
  6. Ventilation and perfusion single photon emission tomography (V/P SPECT) or Quantitative lung perfusion scintigraphy (LPS)
  7. Diaphragm position during exhalation (Comparison of diaphragm apex to rib landmarks using frontal HRCT)
  8. Lung density distribution (post CT image data processing and reconstruction)
  9. St. George's respiratory questionnaire (SGRQ)
  10. Chest X-Ray
5. Variables that were not planned to be documented according to protocol but have been documented:
  1. Pregnancy testing at visit 3 (3months post final Tx) and visit 4 (12 months post Tx1)

2. Static and dynamic pulmonary compliance at Baseline, visit 3 (3months post final Tx) and visit 4 (12 months post Tx1)
6. Due to the small number of patients there will not be any tables presented for secondary endpoints

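### The protocol's visit schedule puts an HRCT and a nuclear lung scan at 12 months without the pregnancy test it marks at every other visit with scheduled radiation

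*Protocol*

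**What the plan says.** Table 3 at the end of Protocol section 4.7.3 has three rows of ionising imaging: chest X-ray, high-resolution CT, and "V/P SPECT or Lung perfusion scintigraphy". It also has a row for pregnancy testing, marked at baseline, Tx1, Tx2 and optional Tx3.

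The only written instruction on timing is in Protocol section 6.5: "Perform pregnancy test for females of child bearing potential prior to radiographic procedures". That section covers the three coil sessions.

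Protocol section 5.2, exclusion 6, rules out women who are pregnant or lactating and those planning a pregnancy during the study.

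SAP section 4, item 5, is headed "Variables that were not planned to be documented according to protocol but have been documented". Its first entry reads "Pregnancy testing at visit 3 (3months post final Tx) and visit 4 (12 months post Tx1".

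**The concern.** The protocol accepts that a woman who could be pregnant should be tested before study radiation, and applies this at every imaging visit but the last. At Visit 4 she would have a CT and a radiotracer with no test planned. Both examinations serve study endpoints (Protocol section 3: lung perfusion, diaphragm position and lung density at 12 months), so the study itself causes the exposure and should carry the safeguard.

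Exclusion 6 does not fill the gap. It deals with pregnancy at entry and with pregnancy plans; an unplanned pregnancy arising during the year would pass it. The eligibility criteria contain no contraception requirement.

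What is at stake is participant safety in a small subgroup. No statistical result depends on it.

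**Working it through.** No figure in the plan needs reproducing. The check sets the rows of Protocol Table 3 side by side against its eight columns.

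| Row | Baseline | Tx1 | Visit 2 | Tx2 | Visit 3 (1 month post Tx2) | Optional Tx3 | Visit 3 (4 months post final Tx) | Visit 4 (12 months) |
|---|---|---|---|---|---|---|---|---|
| Chest X-ray | X | X | | X | | X | | |
| High-resolution CT | X | | | | | | | X |
| Nuclear lung scan | X | | | | | | | X |
| Pregnancy testing | X | X | | X | | X | | **blank** |

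1. Visits with at least one ionising examination: baseline, Tx1, Tx2, Tx3 and Visit 4, that is 5. Fluoroscopy (section 6.5) falls at Tx1 to Tx3 and adds no further visit.
2. Visits with a pregnancy test: baseline, Tx1, Tx2 and Tx3, that is 4.
3. Difference: 5 − 4 = 1, which is Visit 4. Coverage is 4/5, or 3/4 without Tx3.
4. Examinations at Visit 4: one CT + one nuclear scan = 2.

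The four rows above line up with the column headings. Three other rows (still images, compliance and "Bronchoscopy / Coil Placement") appear one column too far right in the text available, with marks under follow-up visits instead of treatment sessions. They are not used in the count.

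An earlier test cannot stand in for one at Visit 4. Taking 12 months as 52 weeks and the intervals in Table 3:

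- Tx2 is 4 to 8 weeks after Tx1, so it precedes Visit 4 by 52 − 8 = 44 to 52 − 4 = 48 weeks.
- Tx3 is 4 to 8 weeks after Tx2, hence 8 to 16 weeks after Tx1, and precedes Visit 4 by 52 − 16 = 36 to 52 − 8 = 44 weeks.

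The last planned test is therefore 36 to 48 weeks old at the 12-month scans. The 8-week limit applies only where possible, so delayed sessions would shorten this somewhat.

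SAP section 4, item 5, gives an independent reading of the same table: it treats testing at Visit 4 as outside the protocol's plan.

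**The case against.** The strongest reply is that practice had already dealt with this. The SAP says Visit 4 testing was documented, so what is left is a table that lags behind conduct. That stands in large part. It is not a full answer, because the SAP does not say whether the test came before the imaging or reached every eligible participant.

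The affected group is also likely to be tiny. The protocol itself remarks, when explaining why transplantation is seldom used, "because of the advanced age of most emphysema patients". This stands too. The number of women of child-bearing potential is not given and may be zero.

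The study ended early, below the planned 60 participants, and SAP section 4, item 4, states that the nuclear-scan data and the CT-derived diaphragm and density data were not entered in the database. The documents therefore cannot show that any Visit 4 exposure took place. Equally, data not entered does not mean scans not done, and the schedule still calls for them.

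Finally, the requirement may be written elsewhere. Protocol section 6.1 says assessments follow the same standards "as those in the pivotal protocol as detailed in the Study Operational Instructions", a document not available here; that sentence concerns assessment standards and does not mention pregnancy testing. The SAP has its own schedule, "Table 1: Visit Schedule", but only its caption could be read. Neither possibility can be excluded, and the fix allows for both.

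**Conclusion.** The point holds as a minor omission in the protocol, not a contradiction within it. One of five visits with scheduled ionising imaging lacks the pregnancy test that the other four have, and that visit carries two examinations. The blank cell is certain, since the SAP reads the schedule the same way.

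The clinical weight is small and cannot be put into numbers: 4 of 5 counts visits and does not measure risk. Whether anyone was exposed without a test cannot be told from the documents. The 6MWD analysis is unaffected. This is a change the sponsor could make, not one on which the trial depends.

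**What to change.** - In Protocol Table 3, mark pregnancy testing at Visit 4 for females of child-bearing potential, to be done before imaging.
- Extend the section 6.5 instruction to that visit, worded so that it covers the nuclear scan as well as the CT.
- First check the Study Operational Instructions and the SAP visit schedule. If either already requires the test, only the protocol needs aligning.
- As a separate editorial matter, name the nuclear scan in the radiation sentence of section 9.1, which now lists only chest X-rays, CT and fluoroscopy.

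The cost is one table entry and one sentence, plus one simple test in what are assumed to be few participants. As Visit 4 testing was already being documented, the added burden is close to nil. The benefit is limited to any remaining 12-month visits (number not given, possibly none) and to future use of this protocol.

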5.1 Inclusion Criteria

Subjects must meet **all** of the following inclusion criteria to be entered into the study:

1. Adult subjects diagnosed with emphysematous type of COPD.
2. CT scan indicates bilateral emphysema, with sufficient lung parenchyma for coil deployment (based on PneumRx CT scoring) criteria.
3. Subject has post-bronchodilator FEV1 \leq 45% predicted.
4. Subject has Total Lung Capacity $>$ 100% predicted.
5. Subject has residual volume (RV) \geq 175% predicted.
6. Subject has marked dyspnea scoring \geq 2 on mMRC scale of 0-4.
7. Subject read, understood and signed the Informed Consent form.
8. Subject has received Pneumococcal and Influenza vaccinations consistent with local recommendations and/or policy.

5.2 Exclusion Criteria

Subjects will be excluded from the study if any of the following conditions apply:

1. Subject has co-morbidities that may significantly reduce subject's ability to improve exercise capacity (e.g. severe arthritis, planned knee surgery) or baseline limitation not due to dyspnea.
2. Subject has a change in FEV1 $>$ 20% (or, for subjects with pre-bronchodilator FEV1 below 1 L, a change of $>$ 200 mL) post-bronchodilator unless investigator can confirm by other means that subject does not have asthma.
3. Subject has severe gas exchange abnormalities as defined by:
 - a. $\text{PaCO}_2 > 55 \text{ mm Hg}$
 - b. $\text{PaO}_2 < 45 \text{ mm Hg}$ on room air (High altitude criterion: $\text{PaO}_2 < 30 \text{ mm Hg}$)
4. Subject has severe pulmonary hypertension defined by right ventricular systolic pressure $>$ 50 mm Hg via right heart catheterization and/or echocardiogram.
5. Subject has evidence of other severe disease (such as, but not limited to, lung cancer or renal failure), which in the judgment of the investigator may compromise survival of the subject for the duration of the study.
6. Subject is pregnant or lactating, or plans to become pregnant within the study timeframe.
7. Subject has an inability to tolerate bronchoscopy under moderate sedation or general anesthesia.
8. Subject has clinically significant bronchiectasis.

9. Subject has had previous LVR surgery, lung transplantation, lobectomy or other BLVR treatment in either lung.
10. Subject has participated in studies to treat COPD using high dose radiation.
11. Subject has been involved in pulmonary drug or device studies within 30 days prior to this study.
12. Subject is chronically taking >20 mg prednisone (or equivalent dose of a similar steroid) daily.
13. Subject requires high level chronic immunomodulatory therapy to treat a moderate to severe chronic inflammatory autoimmune disorder.
14. Subject is on any type of antiplatelet or anticoagulant therapy which cannot be stopped for seven (7) days prior to procedure.
15. Subject has a sensitivity or allergy to Nickel.
16. Subject has a known sensitivity to drugs required to perform bronchoscopy.
17. Subject has been diagnosed with alpha-1 antitrypsin deficiency (AATD).
18. Subject has any other disease, condition(s) or habit(s) that would interfere with completion of study and follow-up assessments, would increase risks of bronchoscopy or assessments, or in the judgment of the investigator would potentially interfere with compliance to this study or would adversely affect study outcomes.

6 Study Plan

